Title:

The effect of audiovisual aids on perioperative stress response, pain and overall experience – a randomized controlled pilot study (AVA Pilot)

NCT# 02506673

Date: 9/18/19

Title:

The effect of audiovisual aids on perioperative stress response, pain and overall experience – a randomized controlled pilot study (AVA Pilot)

What is the condition or intervention to be studied?

The effect of personal audiovisual equipment (audio/video goggles) on perioperative stress, pain and overall experience in patients undergoing ambulatory meniscectomy under spinal anesthesia.

What is/are the research question(s)/specific aim(s)?

- 1) Evaluate the feasibility of the use of personal audiovisual equipment in patients undergoing meniscectomies under spinal anesthesia
- 2) Determine outcome estimates of the use of this equipment on stress levels using skin conductance measurement methodology, request for further sedation, postoperative pain levels and analgesic consumption, time to discharge readiness, and overall patient satisfaction
- 3) Collect thus far unavailable data on the stress response to perioperative stresses (such as IV insertion and spinal placement) in order to allow for power analyses for future studies

What is/are the hypothesis(es)?

- 1) The perioperative use of personal audio visual aids is feasible in the ambulatory surgical arena for meniscectomies under spinal anesthesia
- 2) The use of the audiovisual aid leads to a reduction in perioperative stress, less need for sedatives, lower postoperative pain levels and increased patient satisfaction comparable or superior to a more traditional sedation approach.

Primary outcome will be number of skin conductance responses per second (SCR/sec) and amplitude of skin conductance responses averaged over time in 5 minute intervals and at key time points such before, during and after insertion of an IV, discussion with surgeon, anesthesiologist, immediately before leaving the holding area, immediately after entering the OR, during application of monitors, before and after administration of sedatives, before, during and after spinal insertion, incision, immediately prior to leaving the OR, after arrival at PACU and monitors are placed, before discharge.

Identify and define the secondary outcome(s) and when they will be measured

- Heart rate, blood pressure and respiratory rate absolute and percent change
- Number of requests of additional sedation

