- NRS levels in PACU until discharge and day after surgery

- narcotic consumption in PACU and cumulative over 24 h after PACU discharge pre (after consent) and postoperative (before discharge) anxiety level (State Trait Anxiety Inventory)
- patient satisfaction (Heidelberg Peri-Anaesthetic Questionnaire) in PACU upon spinal resolution
- patient feedback (CSQ8) in PACU upon spinal resolution provider feedback (form sent to providers at end of surgery day)
- Request for sedation/termination of AVA
- complications (headache, transient neurologic symptoms, nausea and vomiting, ...)

Explain why these research questions are being asked:

Little is known about perioperative stress responses and possible anxiety mitigating factors like audiovisual aids or even. IV sedation. Most studies use surrogate markers and retrospective questionnaires, not based on real time gathered data. With skin conductance measurements the sympathetic discharge can be evaluated down to fractions of a second and enables us therefore to continuously monitor stress responses as skin conductance responses/per second during the perioperative management.

What is the background of the topic that you believe is important for the reviewer to know in considering this protocol, including prior studies by this research team. Describe strengths and deficiencies of prior studies; explain how this study fits in. Include references.

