experience feelings of claustrophobia. Similar to computers and video games, when used for prolonged periods of time there are some side effects that users may experience when wearing the video glasses. This includes headaches, dizziness, disorientation or eye twitching. Participants will be made aware of their option to remove the Cinemizer glasses should they experience any unwanted effects.

Per the FDA website: "Nonsignificant risk devices are devices that do not pose a significant risk to the human subjects. Examples include most daily wear contact lenses and lens solutions, ultrasonic dental scalers, and Foley catheters.

A nonsignificant risk device study requires only IRB approval prior to initiation of a clinical study. Sponsors of studies involving nonsignificant risk devices are not required to submit an IDE application to the FDA for approval."

http://www.fda.gov/MedicalDevices/DeviceRegulationandGuidance/HowtoMarketYourDevice/InvestigationalDeviceExemptionIDE/ucm046164.htm#non_sig_risk

Describe your plan for storage and control of experimental devices: The devices used for the study will be stored in a locked cabinet in the Anesthesiology research office. Only study team members will have access to the devices.

Inclusion Criteria:

- Patients scheduled for primary, ambulatory, arthroscopic meniscectomy under spinal anesthesia

Exclusion Criteria:

- Patients with psychiatric disease and those on antidepressants
- Contraindications to spinal anesthesia or allergy to study medication
- Age < 18 years
- Patients with audiovisual impairments prohibiting them from proper use of the study device
- Patients who are blind
- Patients who wear hearing aids
- Patients with inability to communicate in English or understand the study requirements
- Chronic pain patients +/-opioid use
- Patients with (neuro)dermatoses encompassing the hand
- Patients with pacemakers
- Patients with diabetes or known neuropathic disease
- Patients with prior history of claustrophobia
- Patients with prior history of epilepsy or seizure disorder
- Patients undergoing a revision or open procedure

Age Range:

18 and above

Describe how you will identify and recruit potential subjects for participation in the study.

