anesthesiologist with ephedrine, beta blockers or other medications as indicated. Because intraoperative administration of ketorolac, dexamethasone, and periarticular prednisone and morphine could affect pain management, we will record information (dose, amount) about these medications.

Equipment will be removed in the PACU at the patient's request or upon spinal resolution. After spinal resolution, patients will complete the Heidelberg Perianaesthetic Questionnaire. If patients are randomized to the audiovisual equipment group, they will also provide feedback regarding their experience with the audiovisual equipment when they complete the CSQ8 questionnaire. Providers will also receive a survey about the audiovisual equipment at the end of the surgery day.

On POD 1, patients will report their opioid consumption and pain level since discharge.

Data will be collected:

Day of Surgery Preoperatively: from chart and patient interview

- a. Patient demographics – date of birth, race, ethnicity, gender, education level, prior surgeries
- b. State-Trait Anxiety Inventory (STAI) score
- c. NRS pain scores at rest
- d. Start time of Zeiss and HappyMed System audiovisual aids

PACU: from chart and patient interview.

- a. Anxiolytic, hemodynamic and opioid medication consumption (Also recording intraop administration of ketorolac, dexamethasone, and periarticular prednisone and morphine)
- b. End time of Zeiss and HappyMed system audiovisual aids (start and end times will be used to calculate total viewing time)
- c. Type of movie/program viewed on Zeiss and HappyMed System audiovisual aids
- d. NRS pain scores at rest
- e. STAI score
- f. Patient satisfaction (Heidelberg Perianaesthetic Questionnaire score)
- g. Patient feedback regarding use of audiovisual equipment (if randomized to that group)
- h. Provider feedback regarding use of audiovisual equipment (survey sent via email at end of surgery day)

Continuous Throughout Hospital Stay*: MedStorm Stress Detector

- a. Skin Conductance responses per second
- b. Amplitude of skin conductance responses
- c. Heart rate
- d. Blood pressure
- e. Respiratory rate
- f. Complications

Postoperative Day 1: patient interview

- a. NRS pain scores at rest
- b. Opioid medication consumption

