**Certain time points will be flagged in the recordings: before, during and after insertion of an IV, discussion with surgeon, anesthesiologist, leaving holding area, entering OR, application of monitors, administration of sedatives, before, during and after spinal insertion, incision, leaving OR, entry to PACU, resolution of spinal*

NOTE: After conducting the interim analysis and plotting the skin conductance data, we have determined that the graphs are not consistent enough to draw any conclusions. Given the technical difficulties we have encountered with the MedStorm Stress Detector, as well as the labor intensity associated with it, we have decided that we will no longer use it from patient 14 on. We will not mark hand movements, as this data was used to understand the skin conductance data. We will continue to enroll patients to complete this pilot/exploratory study, as the other secondary outcomes in particular, the surveys could provide valuable information. Patient satisfaction questionnaires will be the priority in our data analysis the "new primary outcome."

When the data will be collected?

Data will be collected on the day of surgery in the holding area, during the procedure, in the PACU until discharge, and on post-operative day 1

The following source will be used:

- Medical Records
- Patient
- No Private Office Charts Please specify which private office:
- No Registries

Sample Size and Data Analysis

Patients will be randomly assigned to one of two groups each composed of 15 patients. A computer generated randomization table will be generated by a statistician. A concealed allocation randomization schema will be used with randomization to occur after the patient consents to be in the research study. This is an un-blinded study group assignment is not concealed from the patients and the treating physicians.

1. Audiovisual equipment (Zeiss Cinema ProMED; HappyMed System) in the holding area OR and PACU + 2 mg Midazolam upon arrival in OR
2. Traditional sedation with 2 mg midazolam upon arrival in OR (control)

Phone follow ups, survey administrations and the use of the audiovisual device are not standard of care. The Department of Anesthesiology Research and Education Fund will cover the associated costs.

Instruments and questionnaires to be used on this study:

- CSQ 8
- State-Trait Anxiety Inventory

Describe any risks to participants in the Placebo or No-Treatment Arm of the study:

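### Complications are scheduled for collection only up to discharge from an ambulatory procedure, and the day-1 interview does not ask about them

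*Combined protocol and SAP*

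**What the plan says.** The protocol's form asks the authors to "Identify and define the secondary outcome(s) and when they will be measured". In the list that answers it, one entry is "complications (headache, transient neurologic symptoms, nausea and vomiting" and so on, with no time point. Other entries in that list do run past discharge: pain scores to the day after surgery, and narcotic use over the 24 hours after leaving the PACU.

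In the data-collection list, complications appear once, as "f. Complications" under the heading "Continuous Throughout Hospital Stay*: MedStorm Stress Detector". The inclusion criterion is ambulatory meniscectomy under spinal anesthesia, so that window closes at discharge from the PACU.

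The content of the day-1 contact is stated twice. The procedures text says "On POD 1, patients will report their opioid consumption and pain level since discharge". The list headed "Postoperative Day 1: patient interview" has two items, resting pain score and opioid consumption. The section on timing gives the first day after surgery as the last collection point, and no later contact is described.

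The device risk section says of side effects of the video glasses: "This includes headaches, dizziness, disorientation or eye twitching". The Data Analysis section promises differences with 95% CI for every outcome, which includes complications.

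**The concern.** The plan names specific complications as an outcome, then looks for them only while the patient is in the building. Every patient has a spinal and goes home the same day. If headache, neurologic symptoms or nausea can start after discharge, the scheduled assessments will not find those cases, although study staff already contact each patient the next day.

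What is at stake is the meaning of a descriptive secondary outcome. A reader of the results would see complication rates by arm, with a difference and interval, and nothing to show that they stop at discharge. The note that ends skin conductance recording from patient 14 on gives the remaining secondary outcomes as the reason to continue enrolling, so how completely they are collected matters more than it did at the outset. That note also leaves complications listed under a discontinued device, with no separate source named.

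**Working it through.** **Reading the text.** Three statements, set side by side, settle the scheduling question:

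- Outcome list: complications named, no window.
- Data-collection list: complications appear once, under the hospital stay.
- Day-1 contact: pain and opioid use only, in both the procedures text and the list.

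Followed as written, the plan has no step that asks about a complication after discharge. Medical records and the patient are listed as data sources, but private office charts and registries are marked as not used. A patient could volunteer a symptom on the call, but that is not a planned assessment.

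**Plan's own figure.** There is none to reproduce. The protocol uses descriptive statistics in place of a sample size calculation. The only arithmetic is 2 × 15 = 30, which agrees with the stated maximum enrolment.

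**Illustration of size.** Inputs:

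- n = 15 per arm (Sample Size and Data Analysis section).
- p = true proportion of patients with a complication. Assumed.
- f = share of those whose complication first appears after discharge. Assumed.

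The recordable proportion is q = p(1 − f). The chance of recording at least one event in an arm is 1 − (1 − q)^15.

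With p = 10% and f = 0: 1 − 0.90^15 = 79.4%, expected count 15 × 0.10 = 1.5.

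With p = 10% and f = 0.5: q = 0.05, 1 − 0.95^15 = 53.7%, expected count 15 × 0.05 = 0.75.

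| p | f = 0 | f = 0.25 | f = 0.5 | f = 0.75 | f = 1 |
|---|---|---|---|---|---|
| 5% | 53.7% | 43.6% | 31.6% | 17.2% | 0% |
| 10% | 79.4% | 68.9% | 53.7% | 31.6% | 0% |
| 20% | 96.5% | 91.3% | 79.4% | 53.7% | 0% |

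**Effect on the difference.** If f is the same in both arms, the recorded difference is (1 − f) times the true difference, since p₁(1 − f) − p₀(1 − f) = (1 − f)(p₁ − p₀). At f = 0.5 it is halved.

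**Interval after no events.** The exact two-sided 95% upper limit is 1 − 0.025^(1/n): 21.8% for 0 of 15 and 11.6% for 0 of 30. Either limit would apply only to the rate up to discharge.

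**The case against.** The strongest reply is that the consequences are easily exaggerated. Most of that reply stands.

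- A reader might infer that the trial will report near-zero rates with a falsely reassuring interval. The documents do not support this. Both p and f are assumptions. Even at p = 20% with 80% of onsets after discharge, the chance of at least one recorded event among 30 is 1 − 0.96^30 = 71%. The 11.6% limit requires pooling the arms, whereas the plan compares two arms of 15, where no events gives a limit of 21.8%.
- A reader might infer that the plan cannot detect headache caused by the glasses. The risk section ties those effects to wearing the glasses, and the equipment comes off in the PACU, so headache during wear is inside the scheduled window. Both arms receive a spinal, so missed spinal headache would be expected in both. With 15 per arm, a modest difference would be hard to show even with complete capture.
- A reader might infer that a safety component of the feasibility aim is compromised. No such component is stated, and complications are not among the outcome estimates named in the aims.
- The timing of onset is a clinical premise that the documents do not state.

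It can also be said that the list is loosely built, since it puts complications under a skin conductance detector, and so is weak evidence that later events were meant to be excluded. That is fair, but it only changes the description from a window that ends at discharge to a window left undefined. Under either reading, no one is instructed to ask.

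**Conclusion.** The gap is confirmed by the text: a named secondary outcome has no planned capture after discharge from an ambulatory procedure, and the one later contact does not cover it. If any of these complications first appear between discharge and the day-1 interview, the reported rates and differences will omit them and will probably be too low. That condition is a clinical assumption.

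The size of the shortfall cannot be derived from the documents. The fall from 79% to 54% is an illustration at p = 10% and f = 0.5, and the table shows how far it moves with other inputs. The issue is under-ascertainment of a descriptive secondary outcome in a pilot. It does not touch the original primary outcome or the satisfaction questionnaires that later took priority. It is worth correcting because the correction is cheap.

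**What to change.** Add a short structured item to the day-1 interview list, worded identically in both arms: headache, new neurologic symptoms distinct from operative knee pain, nausea or vomiting, and dizziness since discharge, each yes/no with time of onset. Identical wording matters because the trial is unblinded.

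Define the outcome as events from randomisation to the day-1 interview, and report in-hospital and after-discharge events separately. List complications apart from the MedStorm heading and name their source.

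The cost is a form update and about a minute per call. No visit, treatment or sample size changes. Three limits remain:

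- Patients already called have in-hospital data only and should be reported as such.
- Onsets after day 1 are still missed, so the illustrative 79% would be regained only if every onset after discharge preceded the call.
- If the query cannot be added, the outcome should at least be labelled as complications up to discharge wherever it is reported.

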Is this a pilot study that could lead to a more definitive protocol or different study?

Yes

Experimental:

Randomized

Controlled

Clinical Trial

This is the “gold standard” for clinical research. These prospective studies have at least two groups. Patients meeting strict inclusion/exclusion criteria are enrolled and randomly assigned to receive either an experimental intervention or to receive what is considered to be an acceptable alternative – usually the current standard of care or a placebo (e.g., study of hylauronic acid injection versus cortisone for arthritis).

Specify all devices used on this study:

Investigational

Device Not Yet Approved for use. This device is completely noninvasive.

The HappyMed System is connected to the Zeiss Cinemizer OLED Glasses to play the video content. This use of this device for the study is aligned with the manufacturer's instructions. This device does not pose a significant risk to study participants and therefore does not need an IDE number. Website:

<http://happymed.org/>

Participants will be asked to place sensors with adhesives on the palm of their hands so that measurements from the device can be recorded. This use of this device for the study is aligned with the manufacturer's instructions. This device does not pose a significant risk to study participants and therefore does not need an IDE number. In addition, this device has been used successfully at HSS for two previously conducted studies.

Participants will be asked to wear the glasses before, during, and after their surgery. Participants will have the option to remove the glasses at any time should they feel any discomfort from wearing the glasses. This use of this device for the study is aligned with the manufacturer's instructions. This device does not pose a significant risk to study participants and therefore does not need an IDE number.

Assess the level of risk these devices pose to study participants:

Non-Significant Risks

Justify your risk assessment above:

The devices used for the study do not pose a significant risk to participants due to their noninvasive nature. The devices are being utilized according to the manufacturers' instructions.

As with other audio devices, if the Cinemizer OLED glasses are worn for long periods of time at a very high volume setting hearing may be affected or participants may

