Patients matching the inclusion criteria for this study will be identified the day before surgery. Patients will be approached about the study in the holding area on the day of surgery. Written consent for all patients will be obtained by research staff or co-investigators.

Please select enrollment type from following drop down list:

Over Course of Study

Target Enrollment

What is the maximum number of subject you plan to enroll in this study?

30

How subjects will be identified

- Potential subjects will be identified after a review of medical records of patients under the care of one or more of the study investigators
- Medical records and/or other Institution sources (databases, registries, billing records, pathology reports, and admission logs) will be reviewed to identify potential participants. May involve access of records by individuals not involved in the patient's care.

We will enroll patients scheduled for primary, ambulatory, arthroscopic meniscectomy under spinal anesthesia, as complete surgical anesthesia can be provided to the surgical site and sedation is essentially optional.

After obtaining written informed consent in the holding area, the research staff will attach a skin conductance device to the patients to measure levels of sympathetic discharge (MedStorm Stress Detector). We will administer the State Trait Anxiety Inventory (STAI) immediately after obtaining consent in the holding area and in the PACU before discharge.

Patients will be randomly assigned to one of two groups, each composed of 15 patients:

1. Audiovisual equipment (Zeiss, Cinema ProMED; HappyMed System) in the holding area, OR and PACU + 2 mg midazolam upon arrival in OR
(Patients can choose audiovisual content from a preexisting library of nature programs)
2. Traditional sedation with 2 mg midazolam upon arrival in OR

Patients can change their mind anytime and ask for additional sedatives in 1 mg increments of midazolam. The spinal anesthetic administered will be up to 3.5 cc 1.5% mepivacaine or between 23 cc 2% chloroprocaine at the discretion of the anesthesiologist. There will be standard ASA monitoring with O2 administered via nasal cannula. 4 mg ondansetron and up to 30 mg ketorolac will be administered as per routine. Hemodynamic instability will be treated as per clinical judgment of the attending

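### Total viewing time is derived from a single start and a single end time, so any period with the glasses off and later resumed counts as viewing and the figure can only err upward

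*Combined protocol and SAP*

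**What the plan says.** Under the heading on data to be collected, the preoperative list has one item for the start: "Start time of Zeiss and HappyMed System audiovisual aids". The PACU list has one item for the end: "End time of Zeiss and HappyMed system audiovisual aids". The end item adds in parentheses that "start and end times will be used to calculate total viewing time". The subtraction is implied rather than written out, and end time is not defined.

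The intended span of use is long. The audiovisual arm receives "Audiovisual equipment (Zeiss, Cinema ProMED; HappyMed System) in the holding area, OR and PACU", and the procedures text says that "Equipment will be removed in the PACU at the patient's request or upon spinal resolution".

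Use may stop within that span. The device section says: "Participants will have the option to remove the glasses at any time should they feel any discomfort from wearing the glasses". The risk justification repeats the point: "Participants will be made aware of their option to remove the Cinemizer glasses should they experience any unwanted effects".

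The first specific aim is to "Evaluate the feasibility of the use of personal audiovisual equipment in patients undergoing meniscectomies under spinal anesthesia". No feasibility measure or criterion is given. Viewing time appears in neither the primary nor the secondary outcome list. The secondary outcomes do include requests for sedation or for ending use of the device.

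**The concern.** With one start and one end, a patient who takes the glasses off for the whole OR period and puts them back on in the PACU has the same recorded viewing time as one who wore them throughout. Nothing else in the listed data separates the two. The flagged time points are perioperative events such as line insertion, transfer and spinal placement, with no flag for glasses off or on. They are marked in the skin conductance recordings, which stop from patient 14 on. No playback log is mentioned.

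What is at stake is the description of exposure. Viewing time is the only listed measure of duration of use, and this pilot is meant to inform a later protocol. A figure that can err only upward would make the device look better tolerated than it was. It would also conceal whether wear broke down in the holding area, the OR or the PACU.

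**Working it through.** **Is there a figure to reproduce?** No. The documents give no viewing time, no off-device time and no sample size calculation (descriptive statistics replace it). The check is therefore the algebra of the rule plus an illustration under stated assumptions.

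**Inputs from the documents**
- One start time and one end time per patient (preoperative and PACU data lists).
- 15 patients in the audiovisual arm (sample size section), so at most 15 viewing times.
- Removal allowed at any time (device section and risk justification).

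**Assumed inputs, not in the documents**
- *f*, the fraction of the start-to-end span with the glasses off before use resumes: 0 to 50%.
- *k*, the number of the 15 patients who interrupt, each with the same *f* and with equal spans.

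**Direction.** Recorded viewing = end − start. True viewing = (end − start) × (1 − *f*). Since *f* cannot be negative, recorded viewing is never below true viewing on account of this error.

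**One patient.** Overstatement = 1/(1 − *f*) − 1.

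| *f* | Overstatement |
|---|---|
| 0 | 0% |
| 5% | 1/0.95 − 1 = 5.3% |
| 10% | 1/0.90 − 1 = 11.1% |
| 25% | 1/0.75 − 1 = 33.3% |
| 50% | 1/0.50 − 1 = 100% |

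**Arm mean.** Overstatement = 1/(1 − *k f*/15) − 1.

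| *k* of 15 | *f* | *k f*/15 | Overstatement |
|---|---|---|---|
| 0 | any | 0 | 0% |
| 1 | 25% | 0.0167 | 1.7% |
| 3 | 25% | 0.05 | 5.3% |
| 5 | 50% | 0.1667 | 20.0% |

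These rows are illustrations and not bounds. One patient off for 10% of the span gives 0.7%; all 15 off for 50% gives 100%.

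**Permanent removal.** If a patient takes the glasses off for good and that moment is logged as the end time, there is no error. The plan does not say that this is what end time means. It lists the item under PACU collection and describes removal there, so a patient who stopped for good in the OR could be given a later end time. That error would also run upward.

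**The case against.** The strongest reply is that the bias is conditional. The documents speak of removing the glasses and never of putting them back on, and they give no indication of how often anyone would. Interruption during discussions with clinicians, transfer or spinal placement is conjecture. The case report form is not part of the documents, so a one-line data item may not be the whole derivation. All of this stands. It is why the point is worded as what can happen and not as what has happened. It does not remove the point, because the stated derivation has no term for an interruption and no listed item would supply one.

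A reader might infer that a feasibility result is overstated. The documents do not support that: aim 1 has no metric or threshold, and viewing time is not tied to it. A reader might also infer that viewing time is the only quantitative evidence on use. It is not. Requests to end use are a secondary outcome, and the satisfaction and feedback forms bear on acceptability. What holds is narrower: it is the only listed measure of *duration*, and a count of terminations does not capture pauses.

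Finally, it might be inferred that a null result would be misread as failure of a fully delivered intervention. That is speculative in a descriptive pilot where no planned comparison uses viewing time.

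The objection on cost also has weight. Logging every event with place and reason could require an observer through the OR and PACU, and labor was one reason for dropping the skin conductance device.

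**Conclusion.** The point holds as a limited one. The rule counts any off-then-on gap as viewing, and the error can only be upward. Its size is unknown: 0% if nobody interrupts, and about 2% to 20% for the arm mean in the three tabulated scenarios with interruption, which rest wholly on assumed numbers of patients, assumed off-fractions and equal spans. It affects a descriptive exposure figure in at most 15 patients. It does not touch the original skin conductance outcome, the satisfaction questionnaires now given priority, any between-group comparison or the sample size. It merits correction because duration of use is relevant to aim 1, nothing else listed measures it, and interruptions not noted at the time are unlikely to be recoverable.

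**What to change.** Replace the derivation in the PACU data list with wording to this effect:

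- End time is the time at which the glasses are finally removed, wherever that occurs.
- For any interruption, record the time off and the time on, with the location (holding area, OR or PACU) where staff can note it.
- Total viewing time is the sum of the on-intervals.
- For the audiovisual arm, report total viewing time, its proportion of elapsed time, and the number of interruptions.

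For patients already enrolled without these times, keep end minus start but label it *elapsed device period*. State also whether viewing time is meant to serve as a feasibility measure.

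The cost is a few extra clock times for staff. Keeping location optional, and not requiring a reason for each interruption, avoids the need for a dedicated observer. The downside for the sponsor is that reported viewing time will be lower wherever interruptions occur, and that figures from before and after the change will not be directly comparable.
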